19.4 Protocol Analysis Exclusions

There may be situations wherein the data will be considered non-evaluable and will not be included in the Evaluable Analysis Population.

Data will be excluded from the Evaluable Analysis Population in the following situations:

- 1. Incomplete or incorrect procedure that affects the primary endpoint due to:
 - a. Equipment failure or malfunction (e.g. filter plugs)
 - b. Unanticipated processing failure
 - c. Results of primary endpoint tests are not available

- 2. Protocol deviations that affect the primary endpoint due to:
 - a. Failure to follow collection procedures outlined in the device Operator's Manual, Instructions for Use (IFU) (Package Insert), Manual of Procedure(s), and site SOPs
- 3. Product non-reinfusbale due to:
 - a. Product does not pass quality check for reinfusion (residual WBC, LR-RBC mass recovery, visual inspection, hemolysis, bacterial growth)
- 4. Subject issues
 - a. Participant lost to follow-up or withdrawn from study
 - b. Other participant issues (e.g. inadequate access, reaction, needle abort)

19.5 Missing, Unused, and/or Spurious Data

Please see Statistical Analysis Plan (SAP) for the handling of Missing, Unused and/or Spurious Data.

19.6 Interim Analysis

There will be no interim analysis for the study.

20 STUDY MANAGEMENT

20.1 Ethics

This CIP will be submitted and reviewed by FDA(CBER) IDE committee and Institutional Review Board (IRB). The study will not begin until approvals for the study is received from the FDA and IRB.

20.2 Investigator Responsibilities

20.2.1 Investigator Agreement

Each Investigator will provide the Sponsor a copy of his/her current curriculum vitae and a signed Investigator Agreement, prior to initiation of the study.

20.2.2 Institutional Review Board

The Investigator/study staff is responsible for knowing and adhering to their IRB requirements.

The institution's IRB, or other committee functioning in a similar capacity, will review and approve the CIP, initial and revised ICFs, and CIP amendments. After approval by the IRB, documentation of approval and the approved ICF will be sent to Terumo Blood and Cell Technologies before any subject is enrolled into this study.

20.2.3 Informed Consent

The Investigator is responsible for preparing the written ICF for this study. Terumo Blood and Cell Technologies will provide the Investigator an ICF template. The Investigator may rearrange or reword the contents of this template, or may add other elements or language, provided the meaning and content are not changed or deleted.

Prior to subject participation in this study, the Investigator must obtain written IRB approval for the CIP and the ICF. The approved ICF will clearly reflect the IRB approval date.

All subjects are free to withdraw from participation in this study at any time, for any reasons, specified or unspecified, and without prejudice. The reason for the subject discontinuing or terminating from the study must be recorded on the CRF.

20.2.4 Study Files and Record Retention

The Investigator must retain all study records until notified by the Sponsor that they are no longer needed. The Investigator will also notify the Sponsor in the event he/she relocates, or for any reason desires to dispose of the records.

20.3 Sponsor Responsibilities

20.3.1 General Responsibilities

As per 21 CFR 812, Terumo Blood and Cell Technologies is responsible for selecting qualified investigators and providing them with the information they need to conduct the investigation properly, ensuring quality study conduct and proper monitoring of the investigation, ensuring required approvals are obtained and that significant new information about an investigation is promptly reported to reviewing IRB/EC and government authorities as well as annual reports as required.

20.3.2 Amendments to the Clinical Investigation Plan

Any amendment to the CIP, as deemed appropriate by Terumo Blood and Cell Technologies, will be implemented as the study progresses. Amendments will be submitted to the IRB/EC and /or regulatory bodies as needed/FDA for written approval before implementation.

20.4 Joint Investigator-Sponsor Responsibilities

20.4.1 Access to Information for Monitoring and Auditing

The Investigator and investigative sites will permit trial-related monitoring, audits, IRB/EC review, and regulatory inspections, providing direct access to source data/documents.

Reveos Automated Blood Processing System	
Clinical Investigation Plan: CTS-5085	

In accordance with ICH GCP guidelines, the Sponsor/auditor must have direct access to the subject's source documentation to verify the data recorded in the CRF. The Sponsor is responsible for routine review of the CRFs at regular intervals throughout the study and to verify adherence to the CIP, as well as the completeness, consistency, and accuracy of the data being recorded. The Sponsor/auditor must have access to any subject records needed to verify the entries in the CRFs. The Investigator agrees to cooperate with the Sponsor/auditor to ensure that any problems detected in the course of these monitoring/auditing visits are resolved. This study will be source document verified by the Sponsor as per the criteria outlined in the study management and monitoring plan.

20.4.2 Training

The Sponsor will train applicable study team members as to the device, protocol, and study procedures and will provide updated information as it becomes available during the course of the study, if applicable. The Investigator is responsible for ensuring that additional site personnel that were not trained by the Sponsor receive applicable documents and training.

20.5 Collecting and Recording Data

The Investigator will maintain complete, accurate, legible, and easily retrievable data, and will allow personnel authorized by Terumo Blood and Cell Technologies access to all study data at any time. Such data will also be secured to prevent loss of data. All required data for this study will be recorded from the source documentation onto standardized CRFs.

20.5.1 Source Documents

Source data is all information, original records of clinical observations, or other activities in a clinical study necessary for the reconstruction and evaluation of that trial. Examples of these original documents and data records include study site records, evaluation checklists, and laboratory results.

20.5.2 Case Report Forms

Case report forms will be in electronic data capture (EDC) or paper format.

All data must be recorded in English. Any missing data must be explained.

Completed CRFs will be reviewed and signed by the Investigator. The Clinical Research Associate (CRA) will verify the CRF data with the participant's source data, evaluate the data for accuracy, consistency, and completeness, and will ensure that all forms with missing data and/or errors are ultimately addressed. Accurate and complete CRFs for a participant must be completed in a timely manner.

20.5.3 Data Queries

Data Queries may be used by Terumo Blood and Cell Technologies staff or designee to attempt to correct or clarify missing, incomplete, or illogical data. Queries must be reviewed and signed off by the Investigator or his/her designee.

20.6 Clinical Investigation Plan Compliance

The Investigator is responsible for ensuring the study is conducted in accordance with the procedures and evaluations described in this CIP. A protocol (CIP) deviation is defined as any event where the Investigator or site personnel deviate from the study CIP or study procedures for any reason.

CIP deviations are prohibited during this study, except as described per ISO 14155 Section 5.6.4(c) "Deviations from the CIP to protect the rights, safety and well-being of human subjects under emergency circumstances may proceed without prior approval of the sponsor and the EC – such deviations shall be documented and reported to the sponsor and the EC as soon as possible."

All deviations must be addressed in study source documents and reported to the Sponsor. Requests for deviations, and reports of deviations (if the deviation affects subject's rights, safety and wellbeing, or the scientific integrity of the clinical investigation), will be provided to the IRB/EC per their guidelines. Further details about the handling of CIP deviations will be included in the MOP.

20.7 Suspension or Termination of the Study

For reasonable cause, either the Investigator or the Sponsor may terminate the Investigator's participation in this study, provided a written notice is submitted within the time period provided for in the Clinical Trial Agreement (CTA). In addition, Terumo Blood and Cell Technologies may terminate the study at any time upon immediate notice for any reason, including but not limited to, Terumo Blood and Cell Technologies belief that termination is necessary for the safety of subjects.

20.8 Publication Policy

Terumo Blood and Cell Technologies recognizes the importance of communication of medical study data and encourages the publication of such data in reputable scientific journals and the presentation of such data at scientific seminars and conferences. Any proposed publication or presentation of the data generated from the study must be provided to Terumo Blood and Cell Technologies for timely review in accordance with the terms of the CTA between the Investigator, the Institution, and Terumo Blood and Cell Technologies. Terumo Blood and Cell

Technologies will not, in its scientific publications or promotional material, quote from publications by Investigators without full acknowledgment of the source. For multi-site trials, all Investigators agree not to publish individual site data. All trial data will be published as one or more manuscripts based on the accumulated data from all trial sites.

Rev A	2022-03-15 20:41 GMT			TBCT Record Document Workflow

# **DOCUMENT HISTORY**

Rev No	Date	Description
1.0	28-APR-2022	Original document

Doc No.: TMP-BS-01 Rev No.: 4.0

Revision No. 1.0

Document Date: 28-Apr-2022

Page 4 of 17

# List of Abbreviations

AABB	American Association of Blood Banks	
ADE	adverse device effect	
AE	adverse event	
CIP	Clinical Investigation Plan	
CIR	Clinical Investigation Report	
FDA	United States Food and Drug Administration	
IFU	Instructions for Use	
LR-RBC	Leukoreduced red blood cell	
MedDRA	Medical Dictionary for Regulatory Activities	
PEAE	procedure-emergent adverse event	
RBC	red blood cell	
SAP	Statistical Analysis Plan	
SAS	Statistical Analysis Software	
SD	standard deviation	
SOP	standard operating procedure	
UADE	unanticipated adverse device effect	
WB	whole blood	
WBC	white blood cell	
WHO	World Health Organization	

Confidential Document

Doc No.: TMP-BS-01 Rev No.: 4.0

Revision No. 1.0

Document Date: 28-Apr-2022

Page 7 of 17

#### 1. INTRODUCTION

### 1.1 Study Background

Blood transfusions have been widely used in medical practice since the early 20th century and are the most common procedure during hospital stays in the United States. Patients may receive a unit of whole blood (WB) or individual blood components to treat any particular condition. Whole blood consists of blood components with cellular elements, colloids, and crystalloids.

Having different relative densities, sedimentation rate, and size, blood components can be separated when centrifugal force is applied. This separation is controlled in part by the specific gravities of these components including, in increasing order, plasma, platelets, leukocytes, and RBCs.

The Reveos® Automated Blood Processing System (Reveos System) can process up to four (4) WB units in one run. It combines balancing, centrifugation, component separation, and sealing into one platform. As an automated blood processor, the Reveos System is beneficial in reducing manual blood processing drawbacks including processing time, and variability in the procedures and end product leading to standardized blood component yield and quality.

The aim of this study is to evaluate the in-vivo 24-hour recovery of autologous RBCs produced with the Reveos System and stored for 42 days, in order to meet the FDA's criteria for manufactured RBCs.

# 1.2 Study Design

This is a prospective, open label multicenter study to evaluate whether the LR-RBC derived from WB processing with the Reveos System meet FDA criteria for in vivo 24-hour recovery endpoints. Up to 50 healthy adult volunteers will be enrolled to target 24 evaluable recovery endpoints. Volunteers will be enrolled at 2 centers, with approximately 12 at each center.

An evaluable recovery endpoint is defined as having been collected from an enrolled participant that exhibits normal health status and vital signs as determined by standard American Association of Blood Banks (AABB) blood donation criteria and has also given appropriate informed consent, met all eligibility criteria, did not meet any exclusion criteria described in section 2.3 throughout the duration of the study, and did not have a change in health status which would cause them to fail the inclusion/exclusion criteria at the time of infusion.

Confidential Document

Doc No.: TMP-BS-01 Rev No.: 4.0

Revision No. 1.0

Document Date: 28-Apr-2022

Page 8 of 17

### 1.3 Study Objective

The primary objective of this study is to evaluate whether the LR-RBC derived from WB processed with the Reveos System meet FDA criteria for in vivo 24-hour recovery.

#### 1.4 Outcome Measures

### 1.4.1 Primary Endpoint

The primary endpoint is the 24-hour in vivo RBC recovery. The FDA criteria requires LR-RBC mean 24-hour recovery  $\geq$ 75% with standard deviation (SD)  $\leq$  9% and a one-sided lower confidence limit for the population proportion of RBCs in vivo recovery of 70% with a "success" being LR-RBC recovery >75%. This allows for low recoveries (<75%) in 2/20 or 3/24 volunteers.

#### 2. STATISTICAL METHODOLOGY

### 2.1 General Principles

All analyses will be performed using SAS® software version 9.4. Concomitant medications used to treat AEs will be coded using World Health Organization (WHO) Drug Dictionary Enhanced September 1, 2021 or later. Medical history and AEs will be coded using Medical Dictionary for Regulatory Activities (MedDRA) version 24.1 or later.

Inferential statistical tests will be identified in the post-text tables as being either one or two sided, and the construct of the confidence limits will be defined (e.g. 90% or 95%). A one-sided confidence interval for the proportion of subjects classified as a treatment success will be determined using an exact 95% confidence limit. Asymptotic confidence limits will be presented based on the normal approximation to the binomial distribution for all other presentations.

Continuous parameters will be summarized by n, mean, median, standard deviation (SD), minimum, and maximum. Except for efficacy parameters, 2-sided confidence limits will also be provided for continuous variables. Categorical variables will be summarized by count and percent. The following general conventions will be applied to all data presentations and analyses.

- All mean and median values will be formatted to one more decimal place than the measured value. Standard deviation values will be formatted to two more decimal places than the measured value. Minimum and maximum values will be presented with the same number of decimal places as the measured value
- The number and percentage of responses will be presented in the form XX (XX.X %) where the percentage is in the parentheses

Confidential Document

Doc No.: TMP-BS-01 Rev No.: 4.0

Revision No. 1.0

Document Date: 28-Apr-2022

Page 9 of 17

• All summary tables will include the analysis population sample size (i.e., number of subjects enrolled in the study)

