19 STATISTICAL PLAN

The following section summarizes the statistical methods that will be used in the analysis of the clinical data from this study. Please see Statistical Analysis Plan for full details.

General Considerations for Data Analysis

Inferential statistical tests will be identified in the post-text tables as being either one or two sided, and the construct of the confidence limits will be defined (e.g. 90% or 95%). Asymptotic confidence limits will be presented based on the normal approximation to the binomial distribution for the proportion of subjects classified as a treatment success. Exact confidence intervals will be used for all other presentations. Continuous demographic parameters, such as the subject's age at the time of enrollment, will be summarized using descriptive statistics (N, mean, median, standard deviation, minimum and maximum value, and 95% 2-sided confidence limits).

In addition to examining the demographic and baseline parameters for establishing the poolability of subject data across the 2 clinical sites participating in the study, adherence to the sampling preparation and reinfusion procedure will also be examined and presented as evidence of compliance. The examination for compliance to the study protocol will be performed both on a site-level and a subject-level within sites. Failing to follow the sample handling and preparation procedures could have a demonstrative effect on the results. Including information from reinfusion where the sample was not properly prepared could dampen the results and significantly contribute to the variability and challenge the normality of the distribution of values used for calculating the average recovery values.

The following general conventions will be applied to all data presentations and analyses.

- Summary statistics will consist of the number and percentage of responses in each level for categorical variables, and the sample size (n), mean, median, standard deviation (SD), range, and 95% 2-sided confidence limits for continuous variables.
- All mean and median values will be formatted to one more decimal place than the measured value. Standard deviation values will be formatted to two more decimal places than the measured value. Minimum and maximum values will be presented with the same number of decimal places as the measured value.
- The number and percentage of responses will be presented in the form XX (XX %) where the percentage is in the parentheses.

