The primary endpoint of RBC recovery at 24 hours post-infusion will be used to assess each of the three criteria specified by FDA. The % recovery for analysis will be provided by the site(s), and not derived during analysis. To assess the criteria associated with the percent of samples with at least a 75% recovery, a success or failure for each observed value will be determined. RBC recovery of at least 75% will be deemed a success, and failure otherwise. A one-sided confidence interval for the proportion of successes will be determined using an exact 95% confidence interval. If the one-sided 95% lower confidence limit is greater than 70% the study will have met its primary endpoint, which will be met if no more than 3/24 data points have less than 75% recovery.

Summary statistics and 2-sided confidence intervals will be presented to assess the actual RBC recovery values and to evaluate the remaining criteria specified by FDA.

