#### 2.5 Analyses

### 2.5.1 Primary Endpoint Analysis

The analysis of the primary endpoint will be conducted using the Evaluable Analysis Population.

The primary endpoint of RBC recovery at 24 hours post-infusion will be used to assess each of the three criteria specified by FDA. To assess the criteria associated with the percent of samples with at least a 75% recovery, a success or failure for each observed value will be determined. RBC recovery of at least 75% will be deemed a success, and failure otherwise. A one-sided confidence interval for the proportion of successes will be determined using the Clopper-Pearson exact method for a 95% confidence interval. If the one-sided 95% lower confidence limit is greater than 70% the study will have met its primary endpoint. Summary statistics will be presented to assess the actual RBC recovery values to evaluate the remaining criteria specified by FDA.

Primary endpoint will be reported with single label 24-hour endpoint recovery method. Dual label 24-hour recovery endpoint will also be reported as an exploratory method.

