# 4. CHANGES FROM THE PROTOCOL

	Summary of Changes			
Rationale:	This revision history captures the updates from Version 3.0 / 01 March 2022 of the CIP to Version 1.0 / 28-APR-2022 of the SAP.			
	Significant changes include the following:			
	
 
Changes and clarification were made to the definitions of the analysis populations.
 
The sample size discussion was updated to accommodate over enrollment.
 
The methods discussed for generating confidence intervals is inconsistent in the CIP. A one-sided lower exact 95% confidence limit will be provided for the proportion of treatment successes. Confidence limits presented for continuous demographic and safety parameters will be based on the normal approximation.
 
Dual label method endpoint for 24-hour recovery will also be analyzed which include mean, standard deviation, median, minimum, maximum, proportion of successes, one-side 95% lower confidence limit.
 
Administrative changes, section numbering, typographical error corrections, and minor wording changes for clarity, to make consistent throughout the text, or to make tables consistent with text as a result of these changes have been made and will not be reflected in the table below. These changes did not result in changes to the conduct of the study, so no CIP Amendment was conducted.
 
			
Change	Language from the CIP	Language from the SAP		
Modification	19.3.1 Full Analysis Population	Section 2.3 Study Populations		
	The Full Analysis Population will include all participants enrolled in the trial.	The Full Analysis Population will include all participants enrolled in the study and who met the eligibility criteria. Efforts will be made to obtain complete recovery data from all participants.		

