Revised	Section 19 Statistical Plan  Asymptotic confidence limits will be presented based on the normal approximation to the binomial distribution for the proportion of subjects classified as a treatment success.  Exact confidence intervals will be used for all other presentations.	Section 2.1 General Principles  A one-sided confidence interval for the proportion of subjects classified as a treatment success will be determined using an exact 95% confidence limit. Asymptotic confidence limits will be presented based on the normal approximation to the binomial distribution for a other presentations.  Section 2.5.1 Primary Endpoint Analysis  A one-sided confidence interval for the proportion of successes will be determined using the Clopper-Pearson exact method for a 95% confidence interval.		et 95% e limits on for all			
Revised	Section 19.2.1 Primary Endpoint  Additional exploratory analyses may be performed on estimates of RBC recovery using RBC mass derived from 99mTc radiolabeling.	Section 2.5.1 Primary Endpoint Analysis  Primary endpoint will be reported with single label 24-hour endpoint recovery method. Dual label 24-hour recovery endpoint will also be reported as an exploratory method.					

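### Does the SAP need to restore the two-sided confidence interval for 24-hour recovery that the protocol planned?

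*SAP*

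**What the plan says.** The protocol plans an interval in two places. Section 19.2.1 says of the primary endpoint: "Summary statistics and 2-sided confidence intervals will be presented to assess the actual RBC recovery values". The general conventions in Section 19 call for "range, and 95% 2-sided confidence limits for continuous variables" and make no exception for efficacy.

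The SAP, which is the later document, narrows this. SAP 2.1 states: "Except for efficacy parameters, 2-sided confidence limits will also be provided for continuous variables". SAP 2.5.1 keeps the protocol's sentence on recovery without the intervals: "Summary statistics will be presented to assess the actual RBC recovery values to evaluate the remaining criteria specified by FDA".

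On method, SAP 2.1 first gives the treatment-success proportion an exact limit, then adds: "Asymptotic confidence limits will be presented based on the normal approximation to the binomial distribution for all other presentations". Item 3 of SAP Section 4 puts it differently: "Confidence limits presented for continuous demographic and safety parameters will be based on the normal approximation".

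The change table in SAP Section 4 has one row for Protocol 19.2.1 and one for Protocol 19. The protocol text quoted in the first is only the dual-label sentence, "Additional exploratory analyses may be performed on estimates of RBC recovery using RBC mass derived from 99mTc radiolabeling". The second concerns exact versus asymptotic methods (it includes the protocol's "Exact confidence intervals will be used for all other presentations") and not which variables receive an interval.

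**The concern.** Three things look wrong at first.

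- The outcome seems upside down. A continuous demographic variable such as age gets confidence limits, while the trial's only endpoint gets none for its mean.
- The protocol specified the interval, and the side-by-side change table does not list its removal. A reader who relied on that table would not learn of it.
- SAP 2.1, read literally, sends every limit other than the success proportion to a binomial approximation. That cannot be applied to the mean of a continuous variable, and item 3 of Section 4 says something else.

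If the interval fed a decision, or if its omission hid information, the SAP would have weakened the primary analysis. If the method wording could not be carried out, the programmer would have to guess.

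**Working it through.** **1. The decision rule, reproduced.** The binding limit is the one-sided 95% Clopper-Pearson lower bound for the success proportion, which is the 0.05 quantile of a Beta(x, n − x + 1) distribution. The inputs (n=24, threshold 70%) come from Protocol 19.1 and SAP 2.2.

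- x = 21: Beta(21, 4) gives 70.77%, as both documents state.
- x = 20: Beta(20, 5) gives 65.82%, again as tabulated.

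So at most 3 failures in 24 are allowed. The chance of passing this part when the true success rate is exactly 70% is P(X ≥ 21 | n=24, p=0.70) = 0.0424. None of this uses an interval for mean recovery.

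**2. The other two criteria.** Protocol 19.1 sets them as sample mean at least 75% and sample SD at most 9%. Both are point estimates. No rule in either document compares a confidence limit for the mean with a threshold.

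**3. Size of what is not printed.** Half-width of a two-sided 95% interval = t(0.975, N−1) × SD/√N. The SDs are assumptions: 9 is the largest the criterion allows, and 6 is an illustrative lower value. N=30 is the top of SAP Table 2.

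| N | t quantile | SD 9 | SD 6 |
|---|---|---|---|
| 24 | 2.0687 | 2.0687 × 9/√24 = 3.80 | 2.0687 × 6/√24 = 2.53 |
| 30 | 2.0452 | 2.0452 × 9/√30 = 3.36 | 2.0452 × 6/√30 = 2.24 |

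The quantities needed are n and SD for the width and the mean for the centre. SAP 2.1 reports all three, giving the mean one extra decimal place and the SD two. Nothing is lost that a reader cannot recover.

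**4. Was the removal open?** SAP 2.1 states the exemption outright. Item 3 of Section 4 says the protocol's interval methods were inconsistent, then sets out an exact one-sided limit for success and limits for demographic and safety parameters only. Item 4 lists the dual-label recovery statistics one by one. It includes a one-sided lower limit but no two-sided interval for the mean. These three places agree with one another and read as a deliberate choice. Only the table row is missing.

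**5. The method wording.** The protocol gave the success proportion an asymptotic binomial limit and everything else an exact one. The SAP reversed the pair, and the words about the binomial moved with the asymptotic half. The sentence directly follows the one on the success proportion and makes sense for other proportions. Continuous variables are taken up in the next paragraph of SAP 2.1, and item 3 gives their method. SAP 2.1 states no level for the two-sided limits; Protocol 19 supplies 95%.

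If item 3 is taken to mean a normal rather than a t quantile, the descriptive limits are slightly short. The ratio is 1.9600/2.0687 = 0.9475 at N=24 (5.2% shorter, coverage 93.8%) and 1.9600/2.0096 = 0.9753 at N=50 (2.5% shorter, coverage 94.4%), assuming normal data. This touches demographic and safety summaries only, because recovery gets no such interval.

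**The case for a change.** The best case for a change is that a protocol-specified presentation of the primary endpoint should not disappear without an entry in the table meant to record such things. Section 4 leaves out only administrative and minor wording changes, and this is arguably neither. The mean is judged against 75%, so an uncertainty of 2.5 to 3.8 points is useful beside it. Restoring the interval would cost a table column, and recording its removal would cost one row. That a reader could work it out is a poor excuse for leaving it out.

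Part of this stands. The missing row is a real gap in traceability, and printing the interval would have been good reporting practice. The rest does not carry. The exemption is stated in plain words in the body of the SAP, Protocol 19 refers to the SAP for full details, and the summary items in Section 4 agree with the exemption. The interval would add nothing to the assessment against 75%, because that criterion is the sample mean itself. For example, a sample mean of 77 with SD 9 at N=24 would have limits of about 73.2 and 80.8 (77 ± 3.8) and would still meet the mean criterion.

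On method, preferring t to a normal approximation for descriptive demographic and safety limits is a matter of taste, and neither document requires it.

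**Conclusion.** The passages do differ, and one row is missing from the change table, but the plan needs no change. Following the SAP as written gives the same conclusion on all three criteria, with the same 3-failure rule and the same 0.0424 chance of passing the proportion criterion at a true rate of 70%. The only effect is that a derivable interval is not printed: about ±3.8 points at N=24 if the SD is 9, and ±2.5 if it is 6, both assumed. The loose method sentence in SAP 2.1 is a clerical slip that an analyst would settle by applying the binomial approximation to proportions and item 3 to continuous variables. At most, descriptive limits are 5.2% short at N=24.

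This rests on two readings of the documents: that the mean and SD criteria are point-estimate rules, as Protocol 19.1 words them, and that n, mean and SD of recovery are reported, as SAP 2.1 commits. If a confidence limit for the mean were ever made part of the pass rule, the omission would matter.
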